4.5. Treatment Discontinuation

Patients who discontinue from study treatment prior to Week 12/Visit 6 should complete an End of Study (EOS) visit. The EOS visit should be conducted within 7 days from the last dose of study treatment. Patients may discontinue study treatment and remain in the study. If a patient discontinues study treatment for any reason, the patient should continue to follow the schedule of assessments through the Safety Follow-Up Phone Call with modified assessments at interim visits including Week 12/Visit 6 as follows:

- Number of Panic Attacks
- Columbia Suicide Severity Rating Scale (C-SSRS) ([Oquendo MA 2003](#))
- Efficacy Endpoint Questionnaires
- Exploratory Endpoint Questionnaires (when applicable)
- Concomitant Medications
- Adverse Event Monitoring

Patients will be discontinued from treatment for any of the following reasons:

- An AE that requires permanent discontinuation of study treatment*
- Noncompliance to the protocol
- Investigator decision for any medically appropriate reason or belief that further treatment is undesirable or the risk-benefit profile has become unfavorable
- Patient becomes pregnant
- Patient lost to follow-up
- Termination of the study by the Sponsor
- Voluntary withdrawal of consent by patient

* *AEs leading to the discontinuation of study treatment will be followed until resolution, resolution to baseline or until the event is considered stable or chronic.*

4.6. Study Discontinuation

Patients are free to withdraw from participation in the study at any time, for any reason, and without prejudice. The Investigator must withdraw any patient from the study if the patient withdraws consent and requests to stop participating in the study.

In the event the patient withdraws from the study, if possible, an End of Study (EOS) Visit should occur within 7 days after the last dose of study treatment. Patients may discontinue study treatment and remain in the study (see [Section 4.5](#)).

5. STUDY POPULATION

5.1. Inclusion Criteria

All patients must meet the following criteria for inclusion:

1. Male or female, aged 18 to 60 years old, inclusive, at the time of informed consent.
2. Meets DSM-5 Criteria for Panic Disorder.
3. Documented moderate to severe levels of symptoms at baseline Panic Disorder Severity Scale of 13 or above ([Furukawa TA. 2009](#)).
4. Medically stable on current medication regimen for at least 3 months (including PRN medications), as determined by clinician.
5. Willing to remain on current doses of other psychiatric medications throughout the length of the trial trial.
6. Willing and able to safely stop any of the following medications at least 5 days prior to Visit 2: Inhibitors or inducers of CYP3A4 (erythromycin, ritonavir, telithromycin, rifampin), HMG-CoA Reductase Inhibitors (Simvastatin, Lovastatin, Atorvastatin), Beta Blockers (Timolol eyedrops, Metoprolol), Neuromuscular Blocking Agents (curare-like and depolarizing), Antihypertensive Agents (Prazosin and vasodilators, angiotensin-converting enzyme inhibitors, diuretics, beta blockers, alpha agonists), Inhalation Anesthetics, Disopyramide, Flecainide, Quinidine, Cimetidine, Lithium, Carbamazepine, Phenobarbital, Cyclosporine, Aliskiren, Ramipril and Ramiprilat, aspirin, Theophylline, mTOR inhibitors.
7. Willing and able to avoid consumption of grapefruit, grapefruit juice and Seville oranges within two weeks of screening through the last dose of study treatment.
8. Willing and able to limit consumption of alcohol to three servings per day defined as: 1 serving of beer=12 ounces (5% alcohol content); 1 serving of malt liquor=8 ounces (7% alcohol content); 1 serving of wine=5 ounces (12% alcohol content); 1 serving of distilled spirits=1.5 ounces (40% alcohol content).
9. Willing and able to avoid concomitant administration of sensitive P-glycoprotein substrates (digoxin, fexofenadine, dabigatran etexilate, talinolol, loperamide, vinblastine).
10. Fluent in English.
11. Willing to take HB-1.
12. Willing and able to provide informed consent indicating an understanding of the requirements of the study and a willingness to comply with scheduled visits and all study procedures.
13. Female patients must be surgically sterile (or have a monogamous partner who is surgically sterile), or be at least 2 years postmenopausal, or commits to use 2 acceptable forms of birth control (defined as the use of an intrauterine device (IUD), a barrier method with spermicide, condoms, or any form of hormonal contraceptives) for the duration of the study and for 4 months following the last dose of study treatment. Male patients must be sterile (biologically or surgically) or commit to the use of a reliable

method of birth control (condoms with spermicide) for the duration of the study and for 4 months following the last dose of study treatment. Individuals who are involved exclusively in same-sex relationships are exempt from the birth control requirements but must agree to abide by the recommendations if they do engage in a heterosexual relationship.

14. Female patients who are women of childbearing potential (WOCBP) must have a negative pregnancy test at Screening within 7 days of dosing with study treatment.

5.2. Exclusion Criteria

Patients are to be excluded from the study if they meet any of the following criteria:

1. Severe uncontrolled cardiac disease within 6 months of Screening, including but not limited to uncontrolled hypertension, hypotension (defined as below 90/60); unstable angina; myocardial infarction (MI) or cerebrovascular accident (CVA).
2. Any clinically significant electrocardiogram (ECG) abnormalities at screening.
3. History of atrial flutter, atrial fibrillation or hypertrophic cardiomyopathy.
4. Inadequate hepatic function defined as total bilirubin $>1.5 \times$ the upper limit of normal (ULN) ranges of each institution, aspartate aminotransferase (AST) and alanine aminotransferase (ALT) $>3 \times$ the ULN range of each institution.
5. Inadequate renal function defined as serum creatinine $>1.5 \times$ the ULN range of each institution and/or eGFR <60 .
6. Any clinically significant abnormalities in clinical laboratory assessments as assessed by the investigator.
7. Any other systemic conditions or organ abnormalities that in the opinion of the Investigator may interfere with the conduct and/or interpretation of the current study.
8. Unable to complete neuropsychological testing.
9. Diagnosis of Bipolar I, Bipolar II disorder or Schizophrenia.
10. History of suicidal behaviors including ideation.
11. Current treatment with doses of benzodiazepines that are outside the FDA-approved prescriber's information.
12. Use of tricyclic antidepressants and monoamine oxidase inhibitors (MAOIs) is prohibited.
13. Already on treatment with either telmisartan or verapamil or both.
14. Documented prior drug allergy to either telmisartan or verapamil.
15. Documented contraindication to taking telmisartan or verapamil (eg, Duchenne's muscular dystrophy, myasthenia gravis).
16. Documented moderate to severe substance abuse within the last 6 months (recreational cannabis use is allowed).
17. Pregnant or breastfeeding.

6. STUDY PROCEDURES AND ASSESSMENTS

Time points for assessments to be collected throughout the study can be found in the Schedule of Assessments ([Table 1](#)). A brief description of each assessment can be found below.

6.1. Screening and Treatment Procedures and Assessments

6.1.1. Informed Consent Form

An ICF must be signed by prospective patients prior to initiating any study-specific procedures. Standard of care assessments performed prior to ICF signing may fulfill study eligibility requirements if performed within the screening period.

6.1.2. Inclusion and Exclusion Criteria

Inclusion and exclusion criteria ([Section 5.1](#) and [Section 5.2](#), respectively) will be reviewed for each potential patient. Eligibility assessments will include the Mini International Neuropsychiatric Interview for DSM-5 (MINI) ([Sheehan DV. 1998; Sheehan DV. 1992-2016](#)) and Panic Disorder Symptom Severity Scale (PDSS) ([Furukawa T. 2009](#)). Eligibility will be documented in the electronic case report form (eCRF).

6.1.3. Medical History, Demographics, Neurological and Behavioral Health History

Complete medical history will be obtained, including demographics, neurological and behavioral health information. Demographics will include: Age, Sex, Race, Ethnicity, Education, Gender Identity, Lateral Preference Questions, and Parental Education.

6.1.4. Concomitant Medications and Procedures

At Screening, concomitant medications will be recorded. Assessment of any change in concomitant medications or procedures since the last visit will occur at all further patient visits through safety follow-up.

6.1.5. Physical Exam

Physical exams will be conducted at the time points specified in the Schedule of Assessments ([Table 1](#)). The physical examination at screening will consist of the following body systems:

- **Head, eyes, ears, nose, and throat exam:** inspection, palpation ,and testing, as appropriate.
- **Cardiovascular evaluation:** Auscultation of the carotid arteries and left anterior chest to evaluate heart sounds and possible murmurs.
- **Respiratory assessment:** Observation of inspiration and expiration. Auscultation of breath sounds both anterior and posterior chest.
- **Musculoskeletal assessment:** Muscles, bones, and joints are assessed by functional grouping using techniques of inspection, palpation, and manipulation while the clinician observes responses and reactions.
- **Neurological exam:** Observation of mental awareness. Testing of gross motor function and reflexes.

- **Skin and lymph node check:** Skin tone/pallor and lymph nodes are inspected.

Any abnormal change from the initial screening physical examination must be assessed by the investigator as not clinically significant (NCS) or clinically significant (CS) and recorded in the source document and eCRF.

Any CS change after Visit 2, as determined by the investigator, will be recorded as an AE in source documentation and on the AE eCRF.

6.1.6. Height, Weight, and BMI

Height, weight, and BMI will be collected at screening.

6.1.7. Orthostatic Vital Signs

Orthostatic vital signs check will be performed at the time points specified in the Schedule of Assessments ([Table 1](#)). Orthostatic vital signs should include the following steps based up the Agency for Healthcare Research and Quality procedure ([Tool3F](#)):

1. Instruct the patient on the process of orthostatic blood pressure measurement and its rationale.
2. Assess by verbal report and observation the patient's ability to stand.
3. Have patient lie in bed with the head flat for a minimum of 3 minutes.
4. Measure the blood pressure and the pulse while the patient is supine.
5. Instruct patient to sit for 1 minute.
 - a. Ask patient about dizziness, weakness, or visual changes associated with position change. Note diaphoresis or pallor.
 - b. Check sitting blood pressure and pulse.
 - c. If the patient has symptoms associated with position change or sitting blood pressure $\leq 90/60$, put patient back to bed.
6. Instruct patient to stand.
 - a. Ask patient about dizziness, weakness, or visual changes associated with position change. Note diaphoresis or pallor.
 - b. If patient is unable to stand, sit patient upright with legs dangling over the edge of the bed.
 - c. The patient should be permitted to resume a supine position immediately if syncope or near syncope develops.
7. Measure the blood pressure and pulse 3 minutes after patient stands. Support the forearm at heart level when taking the blood pressures to prevent inaccurate measurement.
8. Assist patient back to bed in a position of comfort.
9. Document vital signs and other pertinent observations on the nursing flowsheet or in the medical record. Note all measurements taken and the position of the patient during each reading.

Subtract values 3 minutes after standing (or if patient cannot stand, then sitting) from lying values. A decline of ≥ 20 mm Hg in systolic or ≥ 10 mm Hg in diastolic blood pressure after 3 minutes of standing indicates orthostatic hypotension. Clinically significant orthostatic hypotension should be treated per standard of care and the Medical Monitor should be contacted.

6.1.8. Clinical Laboratory Tests

The following laboratory parameters will be measured at the time points specified in the Schedule of Assessments ([Table 1](#)) and will be analyzed locally:

- Pregnancy test should be administered for women of child-bearing potential (WOCBP) within 7 days prior to Week 0 and then at each subsequent study visit.
- Comprehensive Metabolic Panel (CMP): albumin, blood urea nitrogen, calcium, carbon dioxide, chloride, creatinine, creatinine phosphokinase, glucose, potassium, sodium, total bilirubin, total protein, alanine aminotransferase (ALT), alkaline phosphatase (ALP), aspartate aminotransferase (AST)
- Complete Blood Count (CBC): white blood cell count, red blood cell count, hematocrit, hemoglobin, mean corpuscular volume (MCV), mean corpuscular hemoglobin (MCH), mean corpuscular hemoglobin concentration (MCHC), red cell distribution (RDW), platelet count, mean platelet volume (MPV), Vitamin B12
- Urinalysis: microscopic examination, specific gravity, pH, protein, glucose, ketones, blood and urobilinogen

6.1.9. Study Treatment Administration

Detailed instructions on the administration of study treatment can be found in [Section 7](#).

6.1.10. Adverse Events (AEs)

All AEs should be captured on the eCRF from Visit 2/Week 0 through the Safety Follow-up visit. Adverse events considered at least possibly related to study treatment should be followed until resolution, return to baseline, or deemed chronic or stable.

All serious adverse events (SAEs) will be immediately reported to the Sponsor from the time of Visit 2/Week 0 (dosing) through the Safety Follow-up/End of Study Visit.

See [Section 8.2](#) for a full description of the collection and reporting of AEs during this study.

6.1.11. Electrocardiogram (ECG)

At Visit 1/Screening, Visit 4/Week 4, Visit 5/Week 8 and Visit 6/Week 12 a standard 12-lead ECG will be conducted. following an approximate 10-minute rest period in all patients and will be interpreted by the Investigator to assess clinical significance.

6.1.12. Weber Test

A Weber Test will be conducted at Baseline/Visit 2 and Visit 6/Week 12. The Weber test is a test of lateralization of auditory function. Tap the tuning fork strongly on your palm and then press the butt of the instrument on the top of the patient's head in the midline and ask the patient where they hear the sound. Normally, the sound is heard in the center of the head or equally in both ears. If there is a conductive hearing loss present, the vibration will be louder on the side with the conductive hearing loss. If the patient does not hear the vibration at all, attempt again, but press the butt harder on the patient's head.

Weber Test results will be documented on the eCRF.

6.1.13. Assessments and Questionnaires

6.1.13.1. Mini International Neuropsychiatric Interview for DSM-5 (MINI)

The Mini International Neuropsychiatric Interview (MINI) is a brief, structured diagnostic interview for the major psychiatric disorders in DSM-5 ([Sheehan DV. 1998](#); [Sheehan DV. 1992-2016](#)). It is routinely used to assess psychiatric diagnoses in clinical trials. The Standard MINI with the additional Attention Deficit Hyperactivity Disorder (ADHD) module will be used at Screening.

6.1.13.2. Placebo-Control Reminder Script (PCRS)

Placebo-Control Reminder Script (PCRS) ([Cohen, EA. 2021](#)) will be administered immediately prior to administering the PDSS at Visits 3-6.

6.1.13.3. Panic Disorder Symptom Severity Scale (PDSS)

The PDSS is a brief clinician rating scale designed to rate severity and treatment progress in individuals diagnosed with Panic Disorder ([Furukawa TA. 2009](#)).

6.1.13.4. Number of Panic Attacks

The patient will be asked “How many panic attacks have you had in the last week?” at Visits 1-6. The clinician will confirm the reported panic attack(s) meet DSM-5 criteria ([APA 2013](#)).

6.1.13.5. Assessment of Overall Sleep Quality

The patient will be asked “During the past month, how would you rate your sleep quality overall?” at Visit 2 and Visits 4-6. This is question #6 from the Pittsburgh Sleep Quality Index ([Buysse DJ. 1989](#)).

6.1.13.6. Columbia Suicide Severity Rating Scale (C-SSRS)

The Columbia Suicide Severity Rating Scale (C-SSRS) ([Oquendo MA 2003](#)) is a suicidal ideation rating scale. The scale identifies behaviors and thoughts that are associated with an increased risk of suicidal actions in the future. The C-SSRS Baseline/Screening version will be conducted at Screening. The C-SSRS Since Last Visit version will be conducted at each post-Screening visit, including Baseline.

If the investigator determines that a patient is at risk of suicide or self-harm, appropriate measures to ensure the patient’s safety and obtain mental health evaluation must be implemented. Patients who meet criteria will be referred to a local psychiatrist for prompt evaluation and also to the National Suicide Prevention Hotline. The patient must immediately be discontinued from the study. The event should be recorded as either an AE or SAE as determined by the investigator and reported within 24 hours to the Sponsor.

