 - Short Form McGill Pain Questionnaire (SF-MPQ) ([Melzack R. 1987](#)) only for patients with a medical history of chronic pain
 - Migraine Disability Assessment Questionnaire (MIDAS) ([Lipton RB. 2001](#)) only for patients with a medical history of migraine
- Patients will be randomly assigned to either the HB-1 or placebo treatments groups and will be provided with study drug each month while on treatment. Patients will be instructed to take the study drug once a day (QD) nightly at bedtime (QHS) with or without food, at the same time each day with a glass of water.
- Patients who discontinue from the study prior to Week 12: End of study visit (EOS) and all EOS assessments should be performed within 7 days following the discontinuation from the study. Patients who discontinue study treatment prior to Week 12: Patients may discontinue study treatment and remain in the study. Complete the EOS study visit and all EOS assessments within 7 days of study treatment discontinuation. The patient should continue to follow the schedule of assessments through the Safety Follow-Up Phone Call with modified assessments at interim visits including Week 12/Visit 6 as follows:
 - Number of Panic Attacks
 - C-SSRS ([Oquendo MA 2003](#))
 - Efficacy Endpoint Questionnaires
 - Exploratory Endpoint Questionnaires (when applicable)
 - Concomitant Medications
 - Adverse Event Monitoring

¹ Safety Follow-up Phone Call is performed approximately 7 days after Visit 6/EOS.

^m Only the PDSS will be repeated at the Week 2 visit.

ⁿ Placebo-Control Reminder Script (PCRS) ([Cohen, EA. 2021](#)). The PCRS will be administered immediately prior to administering the PDSS at Visits 3-6.

^o CogScreen Symbol1Digit Coding Test (SDC) ([Kay G. 1995](#)); SDC to be done twice at Screening/Visit 1 and no passing score is required.

TABLE OF CONTENTS

INVESTIGATOR PROTOCOL APPROVAL	2
SPONSOR PROTOCOL APPROVAL	3
CONTACT INFORMATION.....	4
PROTOCOL SYNOPSIS	5
LIST OF ABBREVIATIONS AND DEFINITIONS OF TERMS.....	18
1. BACKGROUND	20
1.1. Unmet Need	21
1.2. HB-1 for the Treatment of Panic Disorder	22
1.3. HB-1	23
1.4. Telmisartan	23
1.5. Verapamil Hydrochloride	23
1.6. Study Overview	23
2. OBJECTIVES.....	25
2.1. Primary Objective.....	25
2.2. Exploratory Objective.....	25
3. ENDPOINTS	25
3.1. Safety Endpoints.....	25
3.2. Efficacy Endpoints.....	25
3.3. Exploratory Endpoints	25
4. STUDY DESIGN AND DESCRIPTION.....	26
4.1. Study Design.....	26

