4.4. Monitoring of Adverse Events

Safety will be assessed through the monitoring of Adverse Events (AEs), Treatment Emergent Adverse Events (TEAEs), clinical laboratory assessments, ECGs, Columbia Suicide Severity Rating Scale (C-SSRS) ([Oquendo MA 2003](#)), and orthostatic vital signs. Patients will be monitored for safety from the first dose of HB-1 or placebo at study Week 0 through the Safety Follow-up visit. Serious adverse events (SAEs) will be reported immediately to the sponsor and recorded in the eCRF.

Table 2 below provides guidance on the management of known toxicities that have been associated with verapamil or telmisartan monotherapy. If any of the following criteria are met, the subject will have study treatment discontinued and the Medical Monitor must be informed immediately. Subjects may discontinue study treatment, however, and remain in the study (see [Section 4.5](#)). The stopping criteria listed below will also be captured as adverse events (see [Section 8](#)).

Table 2: Subject Specific Stopping Criteria

Cardiac Disorders	
Hypotension	
 SBP <90 mmHg and DBP <60 mmHg for three consecutive readings 10 minutes apart
Orthostatic Hypotension	
 Decline of ≥ 20 mm Hg in systolic or ≥ 10 mm Hg in diastolic blood pressure after 3 minutes of standing.
New-onset 2 nd or 3 rd degree AV block	
 Grade 1 or higher per CTCAE V5.0*
Sick sinus syndrome	
 Grade 1 or higher per CTCAE V5.0
Atrial flutter	
 Grade 1 or higher per CTCAE V5.0
Atrial fibrillation	
 Grade 1 or higher per CTCAE V5.0
New-onset bradycardia	
 Resting heart rate below 50
New-onset tachycardia	
 Resting heart rate above 120

Onset of angina pectoris	
 Grade 1 or higher per CTCAE V5.0
Congestive heart failure	
 Grade 1 or higher per CTCAE V5.0
Pulmonary edema	
 Grade 1 or higher per CTCAE V5.0
Peripheral edema	
 Grade 2 or higher per CTCAE V5.0
General Disorders	
Urticaria	
 Grade 2 or higher per CTCAE V5.0

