7.4. Unblinding Procedure

The study drug blind shall not be broken by the Investigator unless information concerning the study drug is necessary for the medical treatment of the subject. All study assessments and assignment of causality for AEs should be performed, if possible, prior to unblinding. In the event of a medical emergency, if possible, the medical monitor should be contacted before the study drug blind is broken to discuss the need for unblinding.

For unblinding a subject, the study drug blind can be broken via the central randomization system.

The sponsor must be notified as soon as possible if the study drug blind is broken. The date, time, and reason the blind is broken must be recorded in the source documents and the same information (except the time) must be recorded on the eCRF.

If any site personnel are unblinded, study drug must be stopped immediately and the subject must be withdrawn from the study.

No change should be made to any prior assessments or data of any subject after unblinding of his/her treatment assignment.

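### Protocol 6.1.13.6 takes suicide-risk patients out of the study, not just off treatment, so a removal before day 64 leaves no Week 12 data for the treatment-policy estimand

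*Protocol*

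**What the plan says.** **The removal rule.** Protocol 6.1.13.6 schedules the C-SSRS throughout: "The C-SSRS Since Last Visit version will be conducted at each post-Screening visit, including Baseline". If the investigator finds a risk of suicide or self-harm, the patient is referred to a psychiatrist and the hotline, the event goes to the sponsor within 24 hours as an AE or SAE, and "The patient must immediately be discontinued from the study". The section does not mention consent or Section 4.5, and it does not say separately that drug stops.

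**The retention rules.** Protocol 4.5: "If a patient discontinues study treatment for any reason, the patient should continue to follow the schedule of assessments". The reduced schedule covers the panic-attack count, C-SSRS and efficacy questionnaires, and includes Week 12. Protocol 4.4 allows the same for patients taken off drug for cardiac events such as AV block or heart failure: "Subjects may discontinue study treatment, however, and remain in the study". SAP 7.7 expects patients who stop treatment but do not withdraw consent to stay in, and SAP 7.10 handles every intercurrent event by treatment policy.

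**The exit path.** Footnote k of the schedule of assessments treats leaving the study separately from stopping treatment. For those who leave, "all EOS assessments should be performed within 7 days following the discontinuation from the study". SAP 7.2 assigns early-discontinuation visits to an analysis visit by day window, and the Week 12 window opens on day 71 (Table 3).

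**The concern.** A treatment-policy estimand needs outcomes after the intercurrent event. Here the protocol stops collecting them for patients who may be willing to continue. A suicide-risk finding is plausibly related to panic severity and to treatment response, so the values lost are unlikely to be a random subset. The plan itself creates this missingness.

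There is also a safety cost. These are the patients for whom repeat C-SSRS ratings matter most, and the scheduled ratings end after the EOS visit. A patient taken off drug for a cardiac event would still be rated through Week 12.

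**Working it through.** **1. The rules side by side.** A suicide-risk event is recorded as an AE or SAE (6.1.13.6). An AE requiring permanent discontinuation of drug is one of the reasons listed in 4.5, which leads to continued follow-up. The same patient can therefore fall under both sections, one ending participation and the other continuing it. The phrase about any reason in 4.5 cannot be fully literal, because its list also contains loss to follow-up and withdrawn consent. Neither applies to a flagged patient who is still willing to attend.

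**2. Day cutoff.** Inputs: EOS at most 7 days after removal (footnote k); Week 12 window from day 71 and Week 8 window days 43–70 (SAP Table 3).
- Earliest removal whose EOS can fall in the Week 12 window: 71 − 7 = day 64.
- Removal on day 63: latest EOS is 63 + 7 = day 70, in the Week 8 window.
- Protocol 4.6 counts the 7 days from the last dose. If the last dose was the night before removal, removal on day 64 gives 63 + 7 = day 70, also too early. The statement that removals before day 64 lose Week 12 holds on both clocks.

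**3. Flags at scheduled C-SSRS visits** (assumption: visits on their target days).

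| Flag at | Latest EOS | Week 12 value | Gap to day 84 | Later scheduled C-SSRS lost |
|---|---|---|---|---|
| Week 2, day 14 | day 21 | lost | 63 days | 3 |
| Week 4, day 28 | day 35 | lost | 49 days | 2 |
| Week 8, day 56 | day 63 | lost | 21 days | 1 |
| Week 12, day 84 | same visit | kept | – | 0 |

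For Week 12 to be recoverable, the Week 8 visit would have to run 64 − 56 = 8 days late, with EOS a full 7 days after that. SAP 7.2 also gives nominal-visit data precedence, so an EOS in a window that already has its scheduled value adds nothing to the model.

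**4. Power.** Inputs from the sample-size sections: SD 4.5, difference 3.75, 40 per arm, two-sided 0.05.
- SE = 4.5 × √(2/40) = 1.006; 3.75/1.006 = 3.73.
- Power is 96.1% by the normal approximation and 95.7% by the t-test, which reproduces the stated figure of more than 95%.
- With one patient lost per arm (39 each), t-test power is 95.3%.

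**5. Illustrative bias.** Assume one HB-1 patient leaves and would have a placebo-like Week 12 change, 3.75 points short of the HB-1 mean. Assume also compound symmetry with correlation ρ across visits, and a model fitted under missing at random.
- No earlier visit shows the shortfall: bias = 3.75/40 = 0.094 points, or 0.094/1.006 = 0.09 SE.
- One earlier PDSS shows it: (1 − ρ) × 0.094 = 0.047 (ρ = 0.5) or 0.028 (ρ = 0.7).
- Three earlier PDSS show it: the factor is 1 − 3ρ/(1 + 2ρ), that is 0.25 or 0.125, giving 0.023 or 0.012.
- A placebo leaver with the opposite deviation reverses the sign.

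**The case against.** **Two separate paths.** Section 4.5 concerns stopping treatment, while 4.6 and the opening of footnote k concern leaving the study. Section 4.6 requires removal when consent is withdrawn but does not say that is the only ground, so 6.1.13.6 can be read as a specific safety rule feeding the exit path. This stands as far as footnote k goes. A reader might infer that footnote k is contradicted, but it has its own exit path and only sets out what happens after removal. A reader might also take SAP 7.7 to retain everyone who has not withdrawn consent, but its subject is patients who stop treatment. What remains is that a removed patient also stops treatment, has not withdrawn consent, and is needed for the estimand in SAP 7.10.

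**The SAP already plans for this.** It would be too strong to say that the analysis simply rests on missing at random. SAP 7.7 treats missing data as not at random unless there is good evidence otherwise, and names control-based imputation and a tipping-point analysis. That is a real mitigation. However, those analyses are only to be considered if enough data are missing. A handful of removals may not trigger them, and they recover no data.

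**The effect is tiny.** This is largely right. Exclusion criterion 10 bars a history of suicidal behavior or ideation, so flags should be few. Shifting the treatment difference by half an SE through one patient would take about 0.5 × 1.006 × 40 = 20 points, against an assumed baseline mean of 15.

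**Section 7.4 looks like the same fault.** It says "If any site personnel are unblinded, study drug must be stopped immediately and the subject must be withdrawn from the study". A reader might infer that it needs the same change, but the documents do not support that. It also asks that "All study assessments and assignment of causality for AEs should be performed, if possible, prior to unblinding", and PDSS and CGI-S are clinician-rated. Removing the patient keeps possibly unblinded ratings out of the primary analysis, so retention there is a trade-off and not a clear gain.

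**Conclusion.** The inconsistency holds for 6.1.13.6. Its removal rule ignores consent and does not fit Protocol 4.5, SAP 7.7 or SAP 7.10. A removal before day 64 cannot supply Week 12 PDSS, CGI-S or panic-attack values, and scheduled C-SSRS ends after EOS. With on-time visits, flags at Weeks 2, 4 and 8 lose Week 12, and a flag at Week 12 loses nothing.

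The likely numerical effect is small: at most about 0.09 PDSS points per placebo-like HB-1 leaver against an SE of 1.01, and 95.7% to 95.3% power with one patient lost per arm. The bias figure rests on the assumed 3.75-point shortfall and is not a bound. The documents give no removal rate.

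Two stronger inferences are not supported. The result is not seriously threatened at the numbers likely to arise. Nor are these patients left without safety follow-up, since referral, 24-hour reporting and AE follow-up remain. The case for acting is that the missing data are avoidable, are plausibly related to outcome, and cost little to prevent.

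**What to change.** In Protocol 6.1.13.6, keep the referral and the 24-hour reporting, and replace the instruction to discontinue the patient from the study with: *The patient must immediately be discontinued from study treatment. Unless consent is withdrawn or the investigator judges continued visits clinically inappropriate, the patient follows the modified Section 4.5 schedule through Week 12 and the safety call.*

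Leave Section 7.4 as it is.

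Cost: a protocol amendment with IRB handling at the planned 8–10 sites, and possibly a revised consent form. This can wait for the next planned amendment. The visits use a schedule that already exists. Some patients will still leave through the investigator clause, probably including the most unwell, so some outcome-related missingness will remain. The clause is still needed, because whether visits should continue for these patients is a clinical judgment.
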